4.4 Duration of Study

From a study perspective, the anticipated duration of study being open for enrollment will be 2 years. Amongst Fox Chase Cancer Center and its community partners (FCCC) there were 450 analytic (new to the system without ever having had any treatment for their RCC) cases of RCC in 2012 alone and FCCC saw approximately 224 of those cases. Out of these cases at FCCC ~35/year were de novo metastatic and ~30/year were locally advanced and thus at high risk for short-term metastatic progression. In addition, ~30 non-analytic (primary treatment conducted elsewhere) cases per year were seen at FCCC sites.

According to the FCCC RCC database 256 nephrectomies were performed in 2010, 234 in 2011, 227 in 2012 and 204 in 2013. Over 75 new patients with RCC were seen by GU medical oncology in 2013 and over 43 patients with RCC were enrolled on therapeutic clinical trials. Given this volume of patients we believe we can accrue 1-2 patients a month to this trial.

Once an eligible patient is identified and consented, screening will occur within 28 days of study initiation (first day of drug administration). The patient will stay on study unless he or she has PD or unacceptable toxicity or chooses to withdraw consent. Once a patient is no longer on active treatment, follow up for progression and survival will occur for a maximum of 2 years.

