8.1.2 Sample Size Determination

The design incorporates two conditions not usually treated. First, the final group of patients in the phase I component is considered part of the phase II trial. Second, the phase II part has two end-points, toxicity (UT: unacceptable toxicity) and efficacy. The relation between toxicity and efficacy is explicitly taken into account. We test the composite null hypothesis:

$H_0: p(UT) > 0.25 \text{ or } p(PFS > 8 \text{ weeks}) < 0.5 \text{ or } p(PFS > 16 \text{ weeks}) < 0.35$

versus the alternative:

$H_1: p(UT) < 0.05 \text{ and } p(PFS > 8 \text{ weeks}) > 0.66 \text{ and } p(PFS > 16 \text{ weeks}) > 0.56.$

Eleven new patients will be treated in the first stage of the phase 2 component. If 3/17 patients have UTs OR if at most 8/17 are alive and PF at 8 weeks the trial will be either be

suspended for excess toxicity or for futility. The decision for early termination (or amendment) is based on these cut points. If either 3 of 17 stage I patients are DLTs OR if at most 8 of 17 are PF at 8 weeks then terminate or hold up. The final decision point, PFS at 16 weeks is not relevant; the number of such patients does not influence the early decision. The confusion seems to relate to the alternative hypothesis which is couched in terms of 'AND'. It does, of course, require both early and late components of the outcome to be defined. Finally, although 3/17 is less than 0.25, this is the cut point, clearly between 0.05 and 0.25. The early PFS cut point 8/17 is less than 0.5 but is only a cut point.

At that point we will consider protocol amendment. Otherwise, 17 new patients will be recruited. If at least 14/34 patients are PF at 16 weeks AND less than 4/34 have UTs the null hypothesis will be rejected and the treatment declared efficacious. Otherwise it will be declared either too toxic or not efficacious.

Further operating characteristics and statistical details can be found in Appendix 12.3

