12.3 Statistical Considerations and Operating Characteristics for Phase II

Operating characteristics of the design depend on four conditions: toxicity being low (0.05) or high (0.25) and PFS at 16 weeks being low (0.35) or high (0.56). They are summarized below:

1. Toxicity = 0.05 and PFS = 0.56. In this case the power of the study is at least 80%. The chance of early stopping (in error) for excess toxicity is less than 1%. The chance for stopping (in error) for futility varies from 8% to 12% depending on the relation of toxicity to PFS (see details below).
2. Toxicity = 0.05, PFS = 0.35. The chance of early stopping for futility varies from 49% to 57%. The chance of declaring treatment efficacious (type I error) varies from 10% to 21%.
3. Toxicity = 0.25 and PFS = 0.35. Type I error varies from less than 1% to about 5%. Chance of stopping early for either excess toxicity or futility varies from about 26% to about 59%.
4. Toxicity = 0.25 and PFS = 0.56. Type I error varies from about 5% to about 10%. Chance of early stopping for excess toxicity is about 27%.

The term 'UT' here means severe toxicity for which, if frequent enough, dictates dose reduction or trial termination. This early stopping design is an extension of the method of Litwin, Wong and Hudes (Statistics in Medicine, 2007,26:4400-4415). Below, the chance that a patient has a UT and also is PF at 16 weeks is represented by 'a'. 'b', 'c' and 'd', similarly, represent the indicated joint probabilities.

Let $p = p(\text{PFS} > 16 \text{ weeks})$, $p_1 = p(\text{PFS} > 8 \text{ weeks})$ and $p_2 = p(\text{PFS} > 16 \text{ weeks} | \text{PFS} > 8 \text{ weeks})$. Also, let $\text{ptox} = p(\text{UT in 16 weeks})$. Let $\text{ptox1} = f^* \text{ptox} = p(\text{UT in initial 8 week period})$ and $\text{ptox2} = (1-f)^* \text{ptox} = p(\text{UT in 8 through 16 week period} | \text{no UT in the initial 8 weeks})$. Then, $b = p - a$, $c = \text{ptox} - a$ and $d = 1 - a - b - c$. a_1, b_1, c_1 , and d_1 are similarly determined from p_1 and ptox1 . a_2, b_2, c_2 and d_2 are determined likewise, from p_2 and ptox2 .

The table:

$P(\text{UT})$	$1 - p(\text{UT})$	
a	b	$p(\text{PFS} > 16 \text{ weeks}) = 0.56$ (under the alternative hypothesis)
c	d	$p(\text{PFS} < 16 \text{ weeks}) = 0.44$
ptox	$1 - \text{ptox}$	1 ($\text{ptox} = 0.05$ under the alternative hypothesis)

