Illustrates how the joint event probabilities a, b, c and d at the end of the study relate. Namely, if we assign $a = 0.02$ then b, c and d can be determined by subtraction. Here we would get: $b = 0.54$, $c = 0.03$ and $d = 0.41$. For any value of a in $(0, 0.05)$ the other three terms are completely specified. In this design we are considering toxicity to be cumulative. We model the total chance of UT to occur with fraction f in the first interval (0, 8 weeks) and $1-f$ in the final 8 weeks. We have considered fractions $f = 0, 0.25, 0.5, 0.75$ and 1.0 , i.e. $f=0$ implies no toxicity in the first 8 weeks and $f = 1$ implies all toxicity occurs then. The final design is based on $f = \frac{1}{2}$.

P(UT)	1-p(UT)
a1	b1 p(PFS > 8) = 0.66
c1	d1 p(PFS < 8) = 0.34
ptox1	1 - ptox1 1 (ptox1 = ptox2 = 0.025 under the alternative with $f = \frac{1}{2}$) and
P(UT)	1-p(UT)
a2	b2 p(PFS > 16 PFS > 8) = 0.848
c2	d2 p(PFS < 16 PFS > 8) = 0.15
ptox2	1 - ptox2 1

The two tables above characterize the early stopping interval (0, 8 weeks) and final interval (8 weeks, 16 weeks). Numbers in the tables represent the alternative hypothesis. Patients in the initial cohort are represented by the top table (a1, b1, c1, d1) in the initial interval and those who are toxicity and progression free at 8 weeks, hence continue on study are represented by the second table (a2, b2, c2, d2) for their second 8 weeks. Patients recruited into the second cohort, if the study makes it past the first 8 week period, are evaluated only at 16 weeks and are represented by the very first table (a, b, c, d).

The chance of early stopping for excess toxicity, for futility, the chance of final declaration of excess toxicity, the power or type I error were all computed for each of the 4 conditions. Within each of these combinations, the fraction, f, of toxicity born within the first 8 weeks was varied in 5 steps from 0 to 1. We selected the number $f = \frac{1}{2}$ in the belief that toxicity is cumulative and this is the maximum fraction expected to occur in the first half of the trial. Design behavior for $f < \frac{1}{2}$ is ‘better’ than that for $f > \frac{1}{2}$, so is not reported here in detail.

The table below lists the various operating probabilities as functions of ‘a’ for each of the four conditions.

Key:

null = 0: PFS at 16 weeks = 0.35

null = 1: PFS at 16 weeks = 0.56

ntox = 0: Toxicity = 0.05

ntox = 1: Toxicity = 0.25

a: probability that PFS > 16 weeks and patient had UT

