1	1	0.06	0.2690	0.0483	0.5818	0.1006	1.0000
1	1	0.07	0.2690	0.0533	0.5770	0.1002	1.0000
1	1	0.08	0.2690	0.0587	0.5718	0.0997	1.0000
1	1	0.09	0.2690	0.0645	0.5664	0.0990	1.0000
1	1	0.10	0.2690	0.0706	0.5607	0.0981	1.0000
1	1	0.11	0.2690	0.0771	0.5548	0.0970	1.0000
1	1	0.12	0.2690	0.0840	0.5485	0.0957	1.0000
1	1	0.13	0.2690	0.0912	0.5419	0.0941	1.0000
1	1	0.14	0.2690	0.0988	0.5350	0.0923	1.0000
1	1	0.15	0.2690	0.1068	0.5278	0.0901	1.0000
1	1	0.16	0.2690	0.1152	0.5203	0.0877	1.0000
1	1	0.17	0.2690	0.1239	0.5126	0.0850	1.0000
1	1	0.18	0.2690	0.1330	0.5045	0.0819	1.0000

1	1	0.19	0.2690	0.1425	0.4962	0.0786	1.0000
1	1	0.20	0.2690	0.1522	0.4876	0.0749	1.0000
1	1	0.21	0.2690	0.1624	0.4787	0.0710	1.0000
1	1	0.22	0.2690	0.1728	0.4696	0.0668	1.0000
1	1	0.23	0.2690	0.1836	0.4602	0.0625	1.0000
1	1	0.24	0.2690	0.1947	0.4506	0.0580	1.0000
1	1	0.25	0.2690	0.2060	0.4408	0.0533	1.0000

Our analysis above is based on the assumption that toxicity is judged at 8 weeks and again at 16 weeks. In fact, the phase I portion of the study will not last beyond 4 weeks for each patient, so that the initial 3 patients, carried over from phase I, could become UT at 8 weeks. The tables above assume that the number of UTs at 8 weeks (not 4 weeks) is at most one. To account for this possibility, we re-computed the table assuming no restriction on the first 6 patients, but using only the early stopping rules for toxicity at 8 weeks. Thus the initial phase II cohort of all 17 patients in this re-computation are all treated alike. The results are shown in the next table. While the table above allows a smaller chance of toxicity than the actual trial, the table below allows a greater chance of toxicity in the initial phase II cohort. The main difference in the two computations is that the chance of early stopping for UT is about 9% higher under the re-computation conditions (35%) than it is under the top table (27%).

Operating characteristics of design with no restriction on the first 6 patients other than those tested at 8 or 16 weeks.

null	ntox	a	tox	fut	toxend	alpha	cksum
0	0	0.00	0.0082	0.4937	0.0114	0.2106	1.0000
0	0	0.01	0.0082	0.5103	0.0110	0.1862	1.0000
0	0	0.02	0.0082	0.5269	0.0106	0.1633	1.0000
0	0	0.03	0.0082	0.5434	0.0102	0.1421	1.0000
0	0	0.04	0.0082	0.5599	0.0098	0.1227	1.0000
0	0	0.05	0.0082	0.5762	0.0094	0.1049	1.0000

null	ntox	a	tox	fut	toxend	alpha	cksum
0	1	0.00	0.3591	0.2586	0.3197	0.0429	1.0000
0	1	0.01	0.3591	0.2700	0.3100	0.0393	1.0000

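### The stage 1 toxicity stop has no time window in 8.1.2 and is evaluated on weeks 0-8 only in Appendix 12.3; counting all UTs to date would stop a 25%-UT regimen early in 55-69% of trials instead of 36%, at small cost

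*Combined protocol and SAP*

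**What the plan says.** - **The rule (8.1.2).** The stage 1 condition reads "If 3/17 patients have UTs OR if at most 8/17 are alive and PF at 8 weeks". The 8 weeks attaches to the progression-free count; the UT count has no window. The 17 are 6 patients carried over from phase I plus 11 more: "Eleven new patients will be treated in the first stage of the phase 2 component".
- **The evaluation (Appendix 12.3).** "Our analysis above is based on the assumption that toxicity is judged at 8 weeks and again at 16 weeks". The second set of tables, which treats all 17 alike, again applies only the 8-week toxicity rule.
- **The rates under test (12.3).** The key gives "ntox = 1: Toxicity = 0.25" and "ntox = 0: Toxicity = 0.05". The appendix defines ptox as the chance of a UT in 16 weeks, calls toxicity cumulative, and places half of it (f = 1/2) after week 8.
- **The results (12.3).** At UT 5% and PFS 0.56, "The chance of early stopping (in error) for excess toxicity is less than 1" percent. At UT 25% the printed chance of the toxicity stop is 0.2690 in the first tables and 0.3591 in the second.
- **The endpoint (Section 3).** The secondary toxicity endpoint is the UT rate at 8 weeks. Section 4.5, by contrast, withdraws a patient for a UT at any point in the study.
- **Accrual (4.4).** "Given this volume of patients we believe we can accrue 1-2 patients a month to this trial".

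**The concern.** The look falls when the 17th patient reaches week 8. By then most of the others have long passed week 8, so their later UTs are already on record. No section says whether those UTs count.

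If the rule is run as 12.3 models it, recorded grade 4 and 5 events are left out of the decision to treat 17 more patients. If it is run as 8.1.2 is worded, they count, and the early-stopping probabilities in 12.3 do not describe the rule.

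This matters most for a toxic regimen. The final rule in 8.1.2 requires fewer than 4 UTs in 34. If every UT counts at the end, a trial with 3 UTs already among the 17 can succeed only if none of the next 17 patients has one. At a 25% risk that chance is 0.75^17 = 0.8%. At 5% it is 0.95^17 = 42%, so the price of stopping has to be checked as well.

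**Working it through.** **1. Reproduce the plan's figure.** With f = 1/2, the week 0-8 UT risk is 0.25 / 2 = 0.125 or 0.05 / 2 = 0.025.
- P(at least 3 of 17), Binomial(17, 0.125) = 0.3591.
- P(at least 3 of 17), Binomial(17, 0.025) = 0.0082.

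Both match the second set of tables. Requiring at most 1 UT in the first 6 patients gives 0.2690 and 0.0059, the first set. The printed early stop therefore contains no UT after week 8.

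**2. Follow-up at the look.** Assume even accrual, with gaps of 4.35 weeks (1 a month) or 2.17 weeks (2 a month). Patient i has been on study 8 + (17 - i) × gap weeks, and has reached week 16 when (17 - i) × gap is at least 8.
- 1 a month: 17 - i ≥ 2, so 15 of 17.
- 2 a month: 17 - i ≥ 4, so 13 of 17.

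**3. UT risk to date.** In 12.3 only patients free of UT and progression at week 8 enter the second interval. Their probability is b1 = p1 - a/2, where p1 is 8-week PFS (0.66 or 0.50) and a is the joint probability of UT and 16-week PFS. With UT times uniform within each 8 weeks and none after week 16, patient i's risk to date is

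ptox/2 + b1 × (ptox/2) × g_i, where g_i = min(1, (weeks on study - 8)/8).

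Example: ptox = 0.25, p1 = 0.66, a = 0 and full follow-up give 0.125 + 0.66 × 0.125 = 0.2075.

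**4. Chance of at least 3 UTs in 17** (exact, summing over unequal risks):

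| UT | 16-week PFS | a | Week-8 count | To date, 1/month | To date, 2/month |
|---|---|---|---|---|---|
| 25% | 0.56 | 0 | 35.9% | 69.2% | 67.6% |
| 25% | 0.56 | 0.25 | 35.9% | 63.8% | 62.4% |
| 25% | 0.35 | 0 | 35.9% | 62.2% | 60.9% |
| 25% | 0.35 | 0.25 | 35.9% | 56.2% | 55.1% |
| 5% | 0.56 | 0 to 0.05 | 0.8% | 2.8-2.9% | 2.6-2.7% |
| 5% | 0.35 | 0 to 0.05 | 0.8% | 2.1-2.2% | 2.0-2.1% |

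Sensitivity at UT 25%: 53-68% if a week 8-16 UT is recorded only when the patient reaches week 16; 75-81% if progressors stay at risk.

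**5. Patients spared at UT 25%.** Patients spared = 17 × P(trial continues on the week-8 count) × share of those trials already at 3 or more UTs. The first probability is 1 - tox - fut from the second tables; the share comes from simulating the same model (400,000 trials per scenario).
- PFS 0.56, a = 0, 1 a month: 17 × (1 - 0.3591 - 0.0222) × 0.52 = 5.5.
- PFS 0.56, a = 0.25, 2 a month: 17 × (1 - 0.3591 - 0.1830) × 0.43 = 3.3.
- PFS 0.35, a = 0, 1 a month: 17 × (1 - 0.3591 - 0.2586) × 0.44 = 2.8 (using the unrounded share).
- PFS 0.35, a = 0.25, 2 a month: 17 × (1 - 0.3591 - 0.5216) × 0.36 = 0.7.

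The shares run over 43-52% at PFS 0.56 and 36-44% at PFS 0.35.

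**6. Final decision.** The printed end-of-study columns are matched when stage 1 UTs from weeks 0-8 are left out of the final count, so both countings are shown.
- Power (UT 5%, PFS 0.56), all UTs counted at the end: 84.1% to 83.5% (a = 0) and 78.0% to 77.4% (a = 0.05).
- Power, appendix counting: a loss of 1.2-1.5 points. The worst row goes from 80.7% to about 79.6%.
- Wrong success at UT 25%, PFS 0.56, a = 0: about 3.0% to 2.8-2.9% with all UTs counted; 8.9% to about 7% with the appendix counting.

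**The case against.** The strongest reply is that the 8-week basis is a disclosed choice. The appendix states it, and it agrees with the 8-week UT endpoint. That stands: a reader might infer an arithmetic error in 12.3, but the toxicity-stop figures are correct for the rule that 12.3 models. What is missing is a window in 8.1.2, and the 16-week hypothesis gives a reason to prefer the longer count.

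Three other stronger readings also fail.
- *The week-8 count throws away half of the UTs.* Because f = 1/2, this is tempting. But week-8 progressors leave the risk set, so in the stage 1 cohort weeks 8-16 hold 35-40% of the 16-week UTs at PFS 0.56 and 27-33% at PFS 0.35, before allowing for those not yet observed.
- *Toxic regimens are being declared successful.* With all UTs counted at the end, the chance of wrong success hardly moves.
- *Later UTs go unwatched.* Section 4.5 halts the study for more than 1 UT in the final 6 phase I patients, 8.1.2 has a final UT limit, and under 8.1.6 a monitoring committee may review toxicity every 3 months and recommend ending accrual. That review is optional and has no numerical rule, so it softens the gap without closing it.

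Finally, even accrual and uniform UT times are assumptions of this check, not statements in the plan.

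**Conclusion.** The point holds as a mismatch between the worded rule and the evaluated rule, with a cheap improvement available. At UT 25%, counting to date raises the early toxicity stop from 35.9% to 62-69% (PFS 0.56) or 55-62% (PFS 0.35), over accrual of 1-2 a month and all tabulated values of a. The benefit is earlier stopping and fewer patients exposed. It is much smaller at PFS 0.35, where futility already ends many of these trials. The cost is real but small: a wrongful toxicity stop of about 2-3%, and 0.5-1.5 points of power, which takes the appendix's worst row just below its 80% claim. The figures rest on the 12.3 model with f = 1/2, even accrual, uniform UT times within each 8 weeks, none after week 16, and progressors leaving the risk set at week 8. The direction does not depend on the timing or progression assumptions: the lowest sensitivity value is 53%.

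**What to change.** - **8.1.2:** add one sentence stating that the stage 1 stop counts every UT recorded in the 17 patients up to the date of the look. The threshold of 3/17 is unchanged.
- **12.3:** rerun the tables on that count for accrual of 1 and 2 a month, stating the assumptions on UT timing and on who remains at risk.
- **Update all dependent statements in 12.3:** the under-1% wrongful stop (becomes about 2-3%); the 27% early stop and the recomputed 35% (the printed 0.3591 rounds to 36%); the 26-59% early-stopping range in condition 3; the type I error ranges; and the claim of at least 80% power.
- **If the team prefers the week-8 window,** 8.1.2 should say so explicitly and acknowledge that later UTs on record are set aside at the look.

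Cost: one sentence and a rerun of the appendix program. No extra patients, visits or data are needed. The statistical price is the 0.5-1.5 points of power and the 2-3% wrongful stop given above.
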